12.2.2 Planned recruitment rate

Subjects will be recruited throughout the COVID19 pandemic

12.3 Randomisation methods

Patients will be randomized to either PEX+SOC or SOC in a 1:1 ratio using block randomization with varying blocks sizes.

Randomisation will be carried out by the commercial company Sealed Envelope which provides online randomisation. This will be accessed by a designated member of staff who will communicate the treatment allocation to the clinical team.

12.4 Statistical analysis plan

12.4.1 Summary of baseline data and flow of participants

Patient characteristics will be summarised by trial arm and inspected for balance. Patient flow throughout the trial will be summarised using a CONSORT diagram. (**APPENDIX 4**)

12.4.2 Primary outcome analysis

The primary analysis will involve a comparison of the binary outcome ‘50% reduction in at least two inflammation markers’ between the PEX+SOC and SOC trial arms using a chi-squared test. The risk difference (and ratio) will be estimated with a 95% confidence interval. All analyses will be performed on an intention to treat basis.

12.4.3 Secondary outcome analysis

Secondary outcomes will be summarised and compared using suitable statistical methods. For example, binary outcomes may be compared using chi-squared tests and numerical outcomes may be compared using t-tests. P-values from tests of secondary outcomes may be adjusted to account for multiple testing. Appropriate regression methods will be used to perform adjusted analyses or to account for repeated measures.

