- B. Citrate reactions: Some patients treated with PEX present with features of hypocalcaemia (fatigue, paraesthesia, tremor, and hypocalcemia). This is treated with calcium boluses, but offset by a calcium infusion throughout PEX.
- C. Risk of viral transmission: Standard measures to prevent infections resulting from the use of medical products prepared from human blood or plasma include selection of donors, screening of individual donations and plasma pool for specific markers of infection and the inclusion of effective manufacturing steps for the inactivation/removal of viruses. When medicinal products prepared from human blood or plasma are administered, the possibility of transmitting infective agents cannot be totally excluded. However Octaplas LG undergoes a number of additional pathogen inactivation steps and is considered very safe.

The table below summarises the risks, frequencies and mitigations of the IMP(s) and NIMP(s) (delete NIMP if it is not applicable)

Name of IMP(s) / NIMP	Potential risk	Risk Frequency	Risk Management
Octaplas	-Reactions to plasma - -Pathogen transmission	-Severe reactions- grade 4- anaphylaxis <1% -Due to nanofiltration and S/D processing, this is the safest and most effective plasma available	-Any reactions treated with antihistamine, paracetamol and /or hydrocortisone -PEX would be stopped if any severe reaction/anaphylaxis -routine viruses are checked pre PEX.
PEX procedure	Citrate toxicity	10-20% of procedures	IV calcium is run during PEX and added boluses given if required

Vascath insertion	Infection, bleeding, thrombosis	Approx. 10%	Lines are changed weekly to reduce infection, intermediate LMWH given, reducing thrombosis. Bleeding rare as lines inserted by USS
-------------------	---------------------------------	-------------	--

Type A = No higher than the risk of standard medical care

5 Objectives

The rationale of this study is to compare outcomes of patients receiving PEX to those who do not. We hope to ascertain if PEX provides a clinical benefit to expand its use nationally and internationally, as there is currently no treatment which improves the morbidity and mortality of patients with severe COVID-19.

Primary objectives:

To compare reduction in inflammatory markers between Plasma Exchange (PEX) and control groups in patients with severe COVID

Secondary objectives:

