9.4 Subsequent assessments and procedures

9.4.1 Visit schedule and assessments

A schedule of all trial assessments and procedures is set-out in **Appendix 3**.

Day 1- 5

- eligibility check pre PEX if randomised to PEX
- Vitals pre and post PEX (temperature, blood pressure, pulse, respiratory rate and oxygen saturation level) or once daily
- Plasma exchange if randomised to PEX
- assessment of compliance with PEX
- general physical examination
- recording of relevant concomitant medications eg start stop dates of antibiotics, noradrenaline
- Daily routine bloods (FBC, renal, liver function and coagulation screen with fibrinogen)
- Inflammatory markers on D1,D3 &D5 (LDH, CRP, D dimer, ferritin)
- Citrated plasma and serum samples pre and post PEX, or daily for those randomised to SOC to save for VWD screen, ADAMTS13 activity, COVID-19 serology, and multiplex inflammatory markers related to ILs cytokines, interferons, and vascular markers of endothelial injury. Spare samples can be used for COVID-19 related research as authorised by the trial team
- Respiratory parameters: Oxygen requirement, respiratory rate, type of ventilator support-as part of standard of care assessment
- Echocardiogram on D1
- Troponin and BNP on D1
- adverse event collection
- Reactions to Plasma exchange: graded 1-4
- Complications related to central vascath
- Need for antibiotics
- Deterioration requiring ventilation
- Arterial or venous thrombotic event

Reassessment (Day 5-7)

Review of clinical and laboratory parameters by trial team. Consideration of further 5 day block of PEX if clinical and biochemical improvement following initial 5-day block but persistent pro-thrombotic phenotype

*If a patient has a second 5 days of PEX started-follow instructions for day 1-5 above

Follow up Day 6 - 28*

- Vitals (temperature, blood pressure, pulse, respiratory rate)
- general physical examination-weekly
- recording of concomitant medications-related to antibiotics, new cardiac medication, but not all the routine medicines re SOC and not including PRN medications.
- Daily routine bloods (FBC, renal, liver function and coagulation screen with fibrinogen)
- Inflammatory markers, at least 3 x/week (LDH, CRP, D dimer, ferritin)

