- Citrated plasma and serum samples taken at least weekly to 28 days to save for VWD screen, ADAMTS 13 activity, COVID-19 serology, and multiplex inflammatory markers related to ILs cytokines, interferons, and vascular markers of endothelial injury. Spare samples can be used for COVID-19 related research as authorised by the trial team
- Respiratory parameters
- Echocardiography D7
- Troponin/BNP weekly D7, D14, D21, D28
- Adverse event collection
- Need for antibiotics
- Deterioration requiring ventilation
- Arterial or venous thrombotic event

End of study Day 28

- 28 day mortality and outcomes
- Echocardiogram, if available, D28

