10.5 Serious Adverse Events which do not require immediate reporting

SAEs associated with COVID-19 disease do not require recording in the CRF, SAE Recording Log or SAE Reporting Form. However, if the relationship between the IMP and an SAE cannot be ruled out the SAE must be recorded and reported to Sponsor as detailed above.

There is high rate of expected deterioration in this group of patients. Anticipated adverse events/interventions associated with COVID-19 infection which are not required to be captured as an SAE/AE include:

- abnormal pathology results from presentation (including inflammatory markers related to a hyperinflammatory response)
- secondary infection
- renal failure
- cardiac disease e.g. arrhythmias, right heart failure
- intubation and ventilation
- VTE/arterial thrombosis
- end organ damage developing either biochemical e.g. AKI, liver impairment or clinical e.g. Intubation, thrombosis (either venous or arterial such as stroke)
- death from COVID19

This will be captured within the medical notes. These represent SAEs but are anticipated based on the natural history of the COVID-19 disease and so do not require immediate reporting. Mortality will be captured as an endpoint.

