12.2 Sample size and recruitment

12.2.1 Sample size calculation

Mortality of patients on intensive care with COVID-19 has been reported to range from 48% of patients no longer on ITU (ICNARC report on COVID-19 in critical care, 27 Mar 2020) to 86% of patients who required invasive mechanical ventilation (Yang, Lancet Respiratory Medicine, Feb 2020).

We aim to recruit up to 40 patients in total (20 per arm). We will have 80% power to detect a statistically significant difference between the treatment groups at the 5% level assuming that PEX+SOC will reduce inflammation markers in 80% of patients compared to just 20% for SOC if we recruit 20 patients. The power is increased to 99% if 40 patients are recruited. Alternatively, if the effect is lower, e.g. PEX+SOC reduces markers in 65% of patients, then the power will be 85% based on 40 patients.

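### Section 12 plans no infection or procedure-harm analysis, and the adverse-event exemptions mean that a later adverse-event table would under-show infection

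*Combined protocol and SAP*

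**What the plan says.** - **Risks named.** Section 4 lists plasma reactions, citrate toxicity ("10-20% of procedures" in the risk table) and, for the vascath, infection, bleeding and thrombosis at roughly 10%.
- **Data scheduled.** Section 9.4.1 lists for Day 1-5 "Reactions to Plasma exchange: graded 1-4", "Complications related to central vascath", "Need for antibiotics" and adverse events. Antibiotic need and adverse events appear again for Day 6-28. Antibiotics are also recorded as concomitant medication in section 9.4.1 and Appendix 3, in both arms, to Day 28.
- **Capture rules.** Section 10.2 keeps adverse events linked to COVID-19 out of the CRF. Section 10.5 puts "secondary infection" on the list of anticipated events that need not be captured and leaves them in the medical notes. The exception is a serious event for which a relationship to the IMP cannot be ruled out.
- **Analysis.** Section 12.1 has one marker-based primary outcome and six secondary outcomes: ventilation, VWF/ADAMTS13 ratio, cardiac function, thrombosis, kidney injury and mortality. Section 12.4.3 states "Secondary outcomes will be summarised and compared using suitable statistical methods". Section 12.4.4 covers missing data only. Section 12.4.2 puts every analysis on an intention-to-treat basis.

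**The concern.** Infection is a listed risk of the line that PEX requires. Followed as written, the plan gives no between-arm estimate of it, and the usual safety net, an adverse-event table, is weakened at the point of capture.

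The loss may also be uneven. The exception in section 10.5 depends on a relationship to the IMP, which section 7.1 defines as OctaplasLG. Control patients receive none, so it cannot bring a control-arm infection back into the data. The wording also leaves unclear whether an infection from the line, rather than the plasma, would qualify. A table by arm could therefore be incomplete in both arms and incomplete in different ways.

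Section 5 says the trial is meant to inform wider use of PEX. A reader would want to set a fall in markers beside infection, reaction and line-complication rates, and Section 12 does not commit to reporting any of these.

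**Working it through.** **1. Match the listed risks to Section 12.**

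| Risk in section 4 | Scheduled in 9.4.1 | Outcome or analysis in Section 12 |
|---|---|---|
| Plasma reaction | Yes, graded, Day 1-5 and repeat blocks | None |
| Citrate toxicity | No item of its own | None |
| Line thrombosis | Vascath and thrombosis items | Secondary outcome 4, if imaged |
| Line bleeding | No item of its own | None |
| Line infection | Vascath item (Day 1-5 and repeat blocks); antibiotics, both arms, to Day 28 | None |

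**2. Arm sizes and the plan's own power figures.** A total of 20 to 40 at 1:1 gives 10 to 20 per arm. The two-sided 5% pooled formula is

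power = Φ{[d√n − 1.96√(2p̄(1−p̄))] / √(p₁q₁+p₂q₂)}.

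- 80% v 20%, n = 10 per arm: (1.897 − 1.386)/0.566 = 0.90, so 81.7% (stated 80%).
- 80% v 20%, n = 20: 98.9% (stated 99%).
- 65% v 20%, n = 20: 84.9% (stated 85%).

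The stated figures reproduce. They concern the marker outcome only; the plan gives no precision figure for any harm.

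**3. Precision of an antibiotic-start comparison.** The plan gives no rate, so assume 50% per arm, the least favourable case. Half-width = 1.96√(2 × 0.5 × 0.5 / n).

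- n = 20: 1.96 × √0.025 = 0.31, or 31 points.
- n = 10: 1.96 × √0.05 = 0.44, or 44 points.

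**4. Line complications.** The 10% is given for vascath insertion. Reading it as per patient is an assumption.

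- 10 PEX patients: 10 × 0.10 = 1 expected; chance of at least one 1 − 0.9¹⁰ = 65%.
- 20 PEX patients: 20 × 0.10 = 2 expected; 1 − 0.9²⁰ = 88%.
- Exact 95% intervals: 1/10 gives 0.3% to 44.5%; 2/20 gives 1.2% to 31.7%; 0/20 has an upper limit of 16.8%.

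The 10% includes thrombosis, so some of these events already fall under secondary outcome 4.

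**5. Citrate events.** With five exchanges each and no repeat block, 50 to 100 exchanges at 10% to 20% give 5 to 10 events (10 patients) or 10 to 20 (20 patients).

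**6. Would tests help?** Fisher's exact test for 10% v 0% has power 0.2% (10 per arm) or 4.3% (20 per arm). Counts and intervals are useful; tests are not.

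**The case against.** Four stronger readings are tempting, and the documents do not support them.

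- **That the plan compares only benefits.** Ventilation, cardiac function, thrombosis, kidney injury and mortality can each show harm from PEX. Reactions and PEX-line complications arise only in the PEX arm, so for these the gap is an unplanned rate, not a missing comparison.
- **That no harm rate would ever be reported.** Section 16 requires a report in EMA format and section 19 promises that data will be analysed and tabulated. Serious events also go to the sponsor, the TMG (section 14.1) and the annual safety report (section 10.8). General adverse-event and reaction tables would probably appear. They are simply not prespecified.
- **That an adverse-event table could show no infection.** A serious infection possibly related to the IMP is still captured, and a line infection could enter as a vascath complication. The gap is infection attributed to COVID-19.
- **That everything needed is already collected.** Citrate and bleeding have no item of their own, and vascath complications are absent from the Day 6-28 list.

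All of this stands, and it limits the point for reactions and line complications to prespecification. It does not answer the infection point: a final-report table cannot recover events that never entered the CRF.

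**Conclusion.** The point holds for infection as more than missing detail: no analysis is planned, and the capture rules mean that a later table would under-show it, while antibiotic data scheduled in both arms go unused. For reactions, line complications and general adverse events it is a modest prespecification gap.

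The size is descriptive. The infection-related risk difference would carry a half-width of about 31 to 44 points, on the assumption of 50% per arm. About 1 to 2 line complications are expected, on the assumption that 10% is per patient. The change should be made, but the trial's primary conclusion does not depend on it.

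**What to change.** - **Add to 12.1.2 and 12.4.3** a descriptive outcome: at least one new antibiotic agent started after randomisation and up to Day 28. Antibiotics already running at randomisation do not count. Report a risk difference with 95% CI over all randomised, without a significance test, and state how a death before any start is counted.
- **In the same place**, state that plasma-exchange reactions by grade and vascath complications (as collected, Day 1-5 and any repeat block) are tabulated with exact 95% CIs among exposed patients, and recorded adverse events and serious adverse events by arm. Show citrate and bleeding events separately only as far as the adverse-event or reaction text identifies them.
- **In 12.4.2**, limit the intention-to-treat sentence to the efficacy and between-arm comparisons. Otherwise the exposed-only denominators contradict it.

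The cost is plan wording and a few tables, with no new visits or samples. One check is needed: section 9.4.1 mentions antibiotic start and stop dates explicitly for Day 1-5 but not for Day 6-28, so confirm that the CRF records start dates throughout. The downside is that antibiotic starts are an imprecise marker of infection and the decision to start is unblinded; label the result accordingly.

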12.4.4 Sensitivity and other planned analyses

The level of missing data will be reported and sensitivity and/or adjusted analyses performed to account for missing data.

12.5 Interim analysis

No planned interim analysis

13 Record keeping and archiving

At the end of the trial, all essential documentation will be archived securely by the CI and trial sites for a minimum of 25 years from the declaration of end of trial.

Essential documents are those which enable both the conduct of the trial and the quality of the data produced to be evaluated and show whether the site complied with the principles of Good Clinical Practice and all applicable regulatory requirements.

The sponsor will notify sites when trial documentation can be archived. All archived documents must continue to be available for inspection by appropriate authorities upon request.

14 Oversight Committees

14.1 Trial Management Group (TMG)

The TMG will include the Chief Investigator and trial staff. The TMG will be responsible for overseeing the trial. The group will meet regularly monthly and will send updates to PIs.

The TMG will review recruitment figures, SAEs and substantial amendments to the protocol prior to submission to the REC and/or MHRA. All PIs will be kept informed of substantial amendments through their nominated responsible individuals.

15 Direct Access to Source Data/Documents

The investigator(s)/ institution(s) will permit trial-related monitoring, audits, REC review, and regulatory inspection(s), providing direct access to source data/documents. Trial participants are informed of this during the informed consent discussion. Participants will consent to provide access to their medical notes.

16 Ethics and regulatory requirements

The sponsor will ensure that the trial protocol, participant information sheet, consent form, submitted supporting documents have been approved by the appropriate regulatory body (MHRA in UK) and an appropriate research ethics committee, prior to any participant recruitment. The protocol, all other supporting documents including and agreed amendments, will be documented and submitted for ethical and regulatory approval as required. Amendments will not be implemented prior to receipt of the required approval(s).

An annual progress report (APR) will be submitted to the REC within 30 days of the anniversary date on which the favourable opinion was given, and annually until the trial is declared ended. The chief investigator will prepare the APR.

Within 90 days after the end of the trial, the CI/Sponsor will ensure that the main REC and the MHRA are notified that the trial has finished. If the trial is terminated prematurely, those reports will be made within 15 days after the end of the trial.

The CI will supply the Sponsor with a report of the clinical trial which complies with the format as defined by the EMA. This will then be uploaded to EudraCT for availability to the MHRA and a copy of the report will be submitted to the main REC, within 1 year after the end of the trial.

The study will be reviewed and authorised to proceed through urgent regulatory review by UCLH COVID19 Clinical trial group

17 Monitoring requirement for the trial

The sponsor will determine the appropriate level and nature of monitoring required for the trial. Risk will be assessed on an ongoing basis and adjustments made accordingly.

The degree of monitoring will be proportionate to the objective, purpose, phase, design, size, complexity, blinding, endpoints and risks associated with the trial.

18 Finance

No financial interests by CI, PIs or trial management members.

18.1 Insurance

University College London holds insurance against claims from participants for injury caused by their participation in the clinical trial. Participants may be able to claim compensation if they can prove that UCL has been negligent. However, as this clinical trial is being carried out in a hospital, the hospital continues to have a duty of care to the participant of the clinical trial. University College London does not accept liability for any breach in the hospital's duty of care, or any negligence on the part of hospital employees. This applies whether the hospital is an NHS Trust or otherwise.

Participants may also be able to claim compensation for injury caused by participation in this clinical trial without the need to prove negligence on the part of University College London or another party. Participants who sustain injury and wish to make a claim for compensation should do so in writing in the first instance to the Chief Investigator, who will pass the claim to the Sponsor's Insurers, via the Sponsor's office.

Hospitals selected to participate in this clinical trial shall provide clinical negligence insurance cover for harm caused by their employees and a copy of the relevant insurance policy or summary shall be provided to University College London, upon request.

Arrangements must be in place, with the manufacturer, to cover the malfunction and breakdown of the apheresis platform.

19 Publication policy

Access to the final trial dataset

- All individuals involved in the trial will have access to the full dataset

Dissemination policy

- the data arising from the trial will be available to all medical investigators
- that on completion of the trial, the data will be analysed and tabulated and a Final Trial Report prepared
- presentation of results at national/international meetings in the future and submission for peer reviewed publication

20 References

Appendix 2: Pre study assessments

	Screening (Pre-treatment assessment)	Treatment Phase				
Day	Day – 2 to Day -1	Day 1	Day 7	Day 14	Day 21	Day 28
Window of flexibility for timing of visits:			e.g. +/- 2 days	e.g. +/- 2 days	E.g. +/- 3 days	e.g. +/- 3 days
Informed Consent	X					
Medical History	X					
Physical Examination						
Vital Signs	X	X	X	X	X	X
Eligibility confirmation	X	X				
Add ALL Protocol Assessments including bloods/urine, ECGs, scans, c as applicable both trial specific and routine (include separate row for each assessment)	X	X	X	X	X	X
Randomisation	X					
IMP administration		X	X	X	X	X
Adverse Events review	X	X	X	X	X	X
Concomitant Medication review	X	X	X	X	X	X

Appendix 3- Schedule of assessments

	Day 1	Day 2	Day 3	Day 4	Day 5	Day 6	Day 7	Day 14	Day 21	Day 28
FBC	X	X	X	X	X	X	X	X	X	X
Biochemistry	X	X	X	X	X	X	X	X	X	X
Coagulation screen including fibrinogen	X		X		X		X	X	X	X
Inflammatory markers (D Dimer, ferritin, LDH, CRP)	X		X		X		X	X	X	X
Virology testing (Hepatitis A, B,C HIV)	X									
COVID19 Testing	X									

Pregnancy test: serum bHCG	X									
Autoimmune screen: ANA, ENA	X									
Cardiac testing: Troponin/BNP	X				X		X	X	X	X
Procoagulant samples: Pre and post PEX. Daily in non PEX group/following PEX. Including cytokine storm analysis	X	X	X	X	X	X	X	X	X	X
ECG/Echocardia gram	X						X			X
Concomitant mediations eg antibiotics, Noradrenaline	X	X	X	X	X	X	X	X	X	X

Change in respiratory support eg HD oxygen/CPAP/Intubation	X	X	X	X	X	X	X	X	X	X
haemofiltration	X	X	X	X	X	X	X	X	X	X
